8.5.4.2.2 Removing Outliers in Triheptanoin-naïve

Sensitivity analysis will be performed by removing identified outliers in pre- and post-UX007 treatment periods for:

- Annualized event rate of MCEs and MCE hospitalizations
- Annualized duration of event rate of MCEs and MCE hospitalizations

See definition of outlier in section 5.21.

8.5.4.2.3 Alternative Clinical Definitions of MCEs in Triheptanoin-naïve Cohorts

Sensitivity analysis will be performed by using an alternative definition of MCEs in pre- and post-UX007 treatment periods for:

- Rhabdomyolysis MCEs alternatively defined as a patient having CK value ≥ 1000 (5 times the upper limit of normal)
- Hypoglycemia MCEs alternatively defined as a patient having glycemia < 3.89 mmol (recommended by the American Diabetes Association as a level for intervention required in diabetic patients)

8.5.4.3 Analyses of Non-MCE Endpoints in Triheptanoin-naïve Cohort

When the sample size and number of observations are allowed, statistical tests will be performed on the following non-MCE endpoints to assess the statistical significance of change from the baseline to assessments at Months 6, 12, 24, 60, 72, and 84 if applicable, respectively. Two-sided 95% confidence interval and p-value will be presented at these visits.

- Echo variables: EF, ventricle size, and SF: the paired t-test will be used to assess the statistical significance of change from baseline variables. The Wilcoxon signed rank test will be performed if the normality assumption is questionable.
- Clinical biomarkers: the paired t-test will be used to assess the statistical significance of change from baseline variables. The Wilcoxon signed rank test will be performed if the normality assumption is questionable.
- SF-10 PHS and PSS: the GEE model as described in Section 8.1.1 will be used to analyze change from baseline scores.
- SF-12v2 PCS & MCS: the GEE model as described in Section 8.1.1 will be used to analyze change from baseline scores.

Statistical testing of the above endpoints will only be performed at the final analysis when the sample size permits. Summary statistics will be provided by visit at a snapshot analysis due to the anticipated limited number of subjects and number of observations at the time of a snapshot. Two-sided 95% confidence intervals will be presented for change from baseline values at all visits.

8.5.5 CL201-Rollover Cohort: Integrated Analyses for efficacy endpoints

For UX007-CL201 rollover subjects, the long-term effects of UX007 will be assessed through both MCE related endpoints and non-MCE related efficacy parameters using data collected during study period 2, i.e., by integrating data collected from UX007-CL201 and UX007-CL202.

8.5.5.1 Pre- and Post-UX007 MCEs in CL201-Rollover Cohort

Annualized event and duration rates of MCE and by MCE type will be calculated for the three time periods: study period 3 (i.e., 18 months pre-UX007 treatment period), the 18 month CL201 treatment period, and study period 1 (CL202 UX007 treatment period). Within study period 1, annualized event/duration rates will be calculated by 18-month time interval. Summary statistics will be provided for calculated annualized event/duration rates. In addition, annualized event/duration rates will be plotted as box plots over time to show the time trend.

Annualized event rates (AER) and Annualized Event Duration rates (AED) will be analyzed by comparing pre- and post-UX007 treatment period. The pre-UX007 treatment period for UX007-CL201 Rollover subjects corresponds to study period 3.

For subjects who had longer than 18 months of follow up on study (CL202) as of the data cutoff date, MCEs that occurred between UX007 initiation and 18 months post UX007 initiation will be included for calculating number of MCEs and total durations in days of MCEs will be calculated accordingly. For subjects who terminated the study prior to reaching 18 months on study, MCEs that occurred between UX007 initiation and the termination visit will be included for calculating number of MCEs and total durations in days of MCEs will be calculated accordingly. For historical annualized event rate and annualized duration rate observed during study period 3, the data collection period is 18 months (548 days) preceding the date of UX007 initiation. For subject's age less than 18 months at UX007 initiation, the data collection period will be between the birthdate and the date prior to UX007 initiation.

Patient level plots to show all MCEs over time and time-points of start of retrospective period relative to the UX007 initiation and early discontinuation in a subject if applicable will be presented.

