A completed Phase 2 clinical trial (UX007-CL201) evaluated the safety and effectiveness of UX007 in LC-FAOD patients who continued to suffer the effects of LC-FAOD disease despite current therapy. Following completion of a 24-week Treatment Period and 54-week Extension Period, subjects from UX007-CL201 were eligible to continue treatment in this extension study (UX007-CL202). Numerous LC-FAOD patients have also participated, or are actively participating in multiple clinical studies or compassionate use treatment programs with UX007/triheptanoin conducted by various sponsors and investigational sites. This open-label long-term safety extension study will provide an opportunity for these patients and treatment-naïve patients (i.e., naïve to both UX007 and food-grade triheptanoin) with clear unmet need to be treated with UX007 for up to 7 years or until commercial availability of UX007 in any region, whichever occurs first, under a single standardized protocol. The study is designed to obtain long-term safety information and evaluate maintenance of efficacy in a diverse LC-FAOD population.

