7.3.1 Inclusion Criteria

Individuals eligible to participate in this study must meet all of the following criteria:

- 1. Male or female, 6 months of age or older
- 2. Prior participation in a clinical study assessing UX007/triheptanoin treatment for LC-FAOD. Study Sponsors/Collaborators include: Oregon Health & Science University, University of Pittsburgh, and Ultragenyx Pharmaceutical (ClinicalTrials.gov Identifiers: NCT01379625, NCT01461304, and NCT01886378). Patients who received UX007/triheptanoin treatment as part of other clinical studies; investigator sponsored trials (IST); expanded access/compassionate use treatment programs; or patients who are treatment naïve (i.e., naïve to both UX007 and food-grade triheptanoin), have failed conventional therapy and, in the opinion of the Investigator and Sponsor, have documented clear unmet need, may also be eligible at the discretion of the Sponsor.
- 3. Confirmed diagnosis of LC-FAOD including: carnitine palmitoyltransferase (CPT I or CPT II) deficiency, very long chain acyl-CoA dehydrogenase (VLCAD) deficiency, long chain 3-hydroxy-acyl-CoA dehydrogenase (LCHAD) deficiency, trifunctional protein (TFP) deficiency, or carnitine-acylcarnitine translocase (CACT) deficiency. Information

on diagnosis will be obtained from medical records and should include confirmed diagnosis by results of acylcarnitine profiles, fatty acid oxidation probe studies in cultured fibroblasts, and/or mutation analysis.

- 4. Willing and able to complete all aspects of the study through the end of the study, including visits and tests, documentation of symptoms and diet, and administration of study medications. If a minor, have a caregiver(s) willing and able to assist in all applicable study requirements.
- 5. Provide written informed consent (subjects aged ≥ 18 years), or provide written assent (where appropriate) and have a legally authorized representative willing and able to provide written informed consent, after the nature of the study has been explained and prior to any research-related procedures.

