5.2 MCE

Major clinical events (MCE) include skeletal myopathy (rhabdomyolysis), hepatic (hypoglycemia) and cardiac disease (cardiomyopathy) events, and are defined as any visit to the ER/acute care, hospitalization, emergency intervention (i.e. any unscheduled administration of therapeutics at home or in the clinic), or any similar event whether caused primarily by LC-FAOD or by an intercurrent illness complicated by LC-FAOD.

5.3 Study Day 1

For all subjects, study day 1 is defined as the day of the first UX007 dose during Study UX007-CL202. For subjects who previously participated in study UX007-CL201, study day 1 coincides with the last UX007-CL201 visit.

Study Day 1 will be used to calculate the study days for all listings.

5.4 UX007 Treatment Day 1

UX007 treatment day 1 is defined as the day of the first UX007 dose. For subjects who rolled over from UX007-CL201, UX007 treatment day 1 is the day of the first UX007 dose during the UX007-CL201 study. For subjects who were UX007/trihep naïve, UX007 treatment day 1 coincides with study day 1.

UX007 treatment day 1 will be used to calculate days on UX007 for subjects who rolled over from UX007-CL201 and for naïve subjects in select statistical analyses.

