5.6 Subject Cohorts for Presentation

All CL202 subjects will be classified into one of the three non-overlapping cohorts in analysis presentations:

- UX007/trihep naïve subjects. This cohort consists of subjects who had no prior exposure to UX007/trihep before enrolling into CL202. However if a subject participated in a prior UX007/trihep study but was off UX007/trihep for more than two years before enrolling into this study, then this subject will be treated as a naïve subject and historical major clinical events will be collected.
- UX007-CL201 rollover subjects. This cohort consists of subjects who rolled over from UX007-CL201 to UX007-CL202 study.
- Other. This cohort includes subjects unassigned to the above two cohorts, i.e., subjects from [name] Comp sites, OHSU site, eIND program and etc.

A subject may have participated in more than one prior UX007/trihep studies/programs, and the cohort that the subject will be assigned to is determined based on the following priority order: UX007-CL201 rollover subjects and Other.

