6 ANALYSIS POPULATIONS

6.1 Full Analysis Set (FAS)

The full analysis set (FAS) will consist of all subjects enrolled and had at least one post-baseline efficacy assessment. The full analysis set will be used for efficacy analyses.

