8.4.3 Demographic and Baseline Characteristics

Summary statistics will be presented for the Full Analysis Set and by subgroup for the following (but not restricted) parameters

- Gender

- Ethnicity
- Race
- Gestational age at birth
- Age at enrollment (ICF date)
- Age at LC-FAOD diagnosis
- Age at first dose of UX007 (in CL202)
- Age at first dose of UX007 (only for CL201 rollover subjects and UX007/trihep naïve subjects)
- Height at baseline
- Weight at baseline
- BMI at baseline

As only limited demographics data (i.e., date of birth and sex) and LC-FAOD diagnosis and LC-FAOD medical history are entered into the clinical database for subjects who previously participated in the UX007-CL001 or UX007-CL201 study, the UX007-CL001 and UX007-CL201 databases will be integrated with UX007-CL202 database to obtain complete data on demographics , LC-FAOD diagnosis, and LC-FAOD medical history.

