8.5.5.2 Sensitivity Analyses for CL201-Rollover Cohort

8.5.5.2.1 Negative Binomial Regression in CL201-Rollover Cohort

The comparison between pre- and post-UX007 MCE rates will also be performed using a negative binomial regression model, which accounts for different follow-up times, with the time that each subject stays in the study included as an offset in the model. This analytic model estimates the ratio of event rate of the post-UX007 treatment period over that of the pre-UX007 treatment period. The model can be performed using SAS GENMOD procedure where the REPEATED statement is used to account for the within patient comparison. Two-sided 95% confidence interval will be provided for the rate ratio along with the p-value.

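### The CL201-rollover pre/post MCE comparison is conditional on entering CL202, an event at the end of the window being compared, and no planned analysis covers CL201 subjects who did not roll over

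*SAP*

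**What the plan says.** **Who is analysed.** SAP 5.6 defines the rollover cohort: "This cohort consists of subjects who rolled over from UX007-CL201 to UX007-CL202 study". Efficacy is analysed in the CL202 Full Analysis Set, which SAP 6.1 describes as "all subjects enrolled and had at least one post-baseline efficacy assessment". A CL201 subject who never enrolled in CL202 can be in neither.

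**How subjects arrive.** Protocol section 5 gives the route: "Following completion of a 24-week Treatment Period and 54-week Extension Period, subjects from UX007-CL201 were eligible to continue treatment in this extension study".

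**Which periods are compared.** For rollovers, SAP 5.4 states that "UX007 treatment day 1 is the day of the first UX007 dose during the UX007-CL201 study", and SAP 5.3 places CL202 study day 1 at the last CL201 visit. SAP 8.5.5.1 takes as the pre period the 548 days before UX007 initiation (from birth for the youngest subjects). It counts post-treatment MCEs from initiation to 18 months after it.

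**What is estimated.** SAP 8.5.5.1 states: "Annualized event rates (AER) and Annualized Event Duration rates (AED) will be analyzed by comparing pre- and post-UX007 treatment period". On the negative binomial model, SAP 8.5.5.2.1 adds: "This analytic model estimates the ratio of event rate of the post-UX007 treatment period over that of the pre-UX007 treatment period". That model comes with a two-sided 95% confidence interval and a p-value.

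**The concern.** Membership of the cohort is settled at entry to CL202, when the first 18 months on UX007 are essentially over. A CL201 subject who stopped early or declined CL202 drops out of both the pre and the post column, although both periods were at least partly observed. This differs from attrition during CL202. The early-termination sentence in SAP 8.5.5.1 deals with subjects who left after rolling over and does not bring back those who never did.

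Using each subject as their own control removes stable differences in severity. It does not remove selection on within-subject change. If subjects whose MCEs increased on UX007 were less likely to continue, those who remain would show a reduction even when the drug has no effect, and a real effect would look larger than it is. The listed sensitivity analyses (negative binomial, alternative MCE definitions, and the outlier removal named in the SAP change summary) all use the same selected subjects, so none can detect this.

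**Working it through.** The documents give no event rate, effect size or power for this comparison, and no count of CL201 subjects treated or not rolling over. There is no figure to reproduce. Only the timing comes from the documents; everything on size is assumed.

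**1. Timing.** CL201 lasted 24 + 54 = 78 weeks (Protocol section 5), and 78 × 7 = 546 days. The post window is 18 months, 548 days in the SAP's conversion. 546/548 = 99.6%. For a CL201 completer, nearly the whole post window precedes the event that defines the cohort.

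**2. Algebra.** Let f be the share of CL201 subjects who did not roll over and k their post/pre rate ratio. Assume equal pre-UX007 rates in rollovers and non-rollovers, equal observation time, and a true ratio of 1 in all CL201 subjects. Then (1 − f) × RR + f × k = 1, so the ratio among rollovers is RR = (1 − f·k)/(1 − f). For example, f = 0.10 and k = 1.5 give (1 − 0.15)/0.90 = 0.94.

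| f | k = 0.5 | k = 1 | k = 1.5 | k = 2 |
|---|---|---|---|---|
| 5% | 1.03 | 1.00 | 0.97 | 0.95 |
| 10% | 1.06 | 1.00 | 0.94 | 0.89 |
| 20% | 1.13 | 1.00 | 0.88 | 0.75 |
| 30% | 1.21 | 1.00 | 0.79 | 0.57 |

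The bias is zero when non-rollovers changed as the others did (k = 1), favours UX007 when they did worse, and goes against UX007 when they did better.

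**3. Simulation under no effect.** Gamma-Poisson counts, mean 1 to 2 MCEs per year, gamma shape 0.5 to 2, and 1.5 years on each side. Leaving depends on whether a subject's post count exceeds the pre count.

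| Probability of not rolling over | Rate ratio among rollovers |
|---|---|
| 5–10% if events did not rise, 25–50% if they did (10–26% leave overall) | 0.79–0.96 |
| 15% for everyone | 1.00 |
| 25% if events did not rise, 10% if they did | 1.05–1.08 |

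The first row assumes that subjects whose events rose were 2.5 to 10 times as likely to leave (25/10 to 50/5). In a separate run where leaving depended only on stable severity, the ratio was 1.00.

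**4. If the post window is longer.** SAP Table 11.1.1 lists the rollover MCE analysis under periods 2 and 3, and period 2 runs to the end of CL202. With an assumed 4 further years of CL202 in the post period, the first row becomes 0.87–0.97: diluted, not removed.

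**The case against.** The strongest case against rests on five points.

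- *No outcome-dependent leaving is shown.* A reader might infer that the cohort is selected on the MCE outcome and that the ratio therefore favours UX007. The documents do not support that. Selection is on entering CL202. Neither document says why any CL201 subject left, and the CL201 stopping rule is not given. Protocol 7.3.3.1 and 7.5.2.3 do ask the investigator to consider discontinuation when major events change in nature or become more frequent, but those are CL202 rules. They make bias toward UX007 plausible and no more. This objection stands against any claim of direction.
- *Completion of CL201 is not required.* A reader might also infer that only completers are included. Completion is the expected route, but inclusion criterion 2 asks only for "Prior participation in a clinical study assessing UX007/triheptanoin treatment for LC-FAOD", so an early leaver could qualify. This stands too.
- *The analysis is not primary.* The primary analysis is a descriptive MCE rate over study period 1 in the FAS (SAP 8.5.1), and Table 11.1.1 lists the rollover MCE analysis as descriptive. True, and it limits the severity. But the note under that table leaves the sensitivity analyses to 8.5.5.2, where the ratio and p-value remain.
- *CL201 has its own comparison.* Protocol 5.2.3 cites results for 78 weeks before against 78 weeks on UX007. An all-CL201 analysis would partly repeat it, and the CL202 rollover estimate legitimately describes continuers. That argues for adding an analysis, not for replacing the planned one.
- *The data integration is narrower than it looks.* SAP 8.4.3 says that "the UX007-CL001 and UX007-CL201 databases will be integrated with UX007-CL202 database", but the purpose there is demographics, diagnosis and medical history for subjects with prior participation. SAP 8.5.5 integrates efficacy data for rollovers only. MCE data for non-rollovers would have to be brought in.

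**Conclusion.** The point holds as a conditional one. The comparison in SAP 8.5.5.1 and 8.5.5.2.1 is restricted by an event that, under the window described in 8.5.5.1, falls at the end of the period being compared, and no planned analysis shows what that restriction does. Bias toward UX007 is plausible, but its size and sign cannot be determined from the documents. The ratios of about 0.8 to 0.95 under no effect depend entirely on assuming that subjects with rising events left more often. Over the wider assumed range in the algebra (f 5–30%, k 0.5–2), a true ratio of 1.00 would appear as anything from 0.57 to 1.21. If few CL201 subjects failed to roll over, or their MCE rates changed as the others' did, the issue is negligible. The SAP does not ask for the counts that would show this. It is worth correcting, but it does not touch the primary analysis.

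**What to change.** 1. Keep the rollover analysis in SAP 8.5.5.1 and 8.5.5.2.1, and label it as conditional on entry to CL202.
2. Add to SAP 8.5.5.2 a sensitivity analysis of all subjects treated in CL201 over matched windows: up to 18 months before UX007 (from birth where applicable) against the first 18 months on UX007. Use the same negative binomial model, with each subject's actual person-time in each period, up to discontinuation, as the offset. Show it beside the rollover-only result. Matched windows are preferable to pooling all CL201 and CL202 time, which gives continuers more weight: under the no-effect model with 4 CL202 years, pooling still gave 0.95–1.00.
3. Report how many CL201 subjects did not enter CL202, the reasons, and their pre/post MCE rates.
4. State in 8.5.5.1 whether 18 months on study means time in CL202 or time since UX007 initiation, and align the study periods in Table 11.1.1.

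**Cost.** SAP wording and some programming to bring in CL201 MCE data for non-rollovers, with no new data collection if the completed CL201 database holds those records. The added analysis partly overlaps CL201's own 78-week comparison, and the estimate may be less favourable. It reduces the selection but cannot recover what happened after a subject stopped treatment.

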5.10.1 Study Period 1 (Main Study Period)

Study period 1, or the main study period, starts from study day 1 till the last visit day in CL202. The last visit date is the last date among the early termination visit date, the study completion visit date, the safety follow up visit date, or the last visit date as of a clinical cutoff date, if applicable. Study period 1 will be used for all efficacy on FAS and safety analyses unless otherwise specified.

5.10.2 Study Period 2

Study period 2 has the same ending date as Study period 1 but starts from UX007 treatment day 1. Study period 2 will be used in select analyses for UX007-CL201 rollover subjects.

[figure not shown]
5.10.3 Study Period 3

Study period 3 starts from the 18 months (548 days) preceding UX007 treatment day 1 and ends 1 day prior to UX007 treatment Day 1. Study Period 3 is referred as the retrospective period for MCE data collection.

Study period 3 will be used for UX007-CL201 rollover subjects and UX007/trihep naïve subjects only in select analyses.

The following figure illustrates the definitions of the three study periods.

Figure 5.10.3.1: Diagram of Study Periods in CL202

Study Period 1 is defined for all enrolled subjects in CL202; Study Period 2 is defined for CL201 rollover subjects only; Study Period 3 is defined for CL201 rollover subjects and UX007/trihep naïve subjects. CL201 treatment period exists for CL201 subjects only;

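### The CL201-rollover pre/post MCE comparison (SAP 8.5.5.1) stops counting 18 months after the first CL201 dose, so it leaves out almost all CL202 follow-up for subjects who stay in the study and depends on dropout for the rest

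*SAP*

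**What the plan says.** SAP 8.5.5 says the rollover analyses assess long-term effects on MCE and other endpoints over study period 2, integrating CL201 and CL202. Table 11.1.1 lists periods 2 and 3 for the rollover MCE rows. SAP 5.10.2 defines that period: "Study period 2 has the same ending date as Study period 1 but starts from UX007 treatment day 1".

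SAP 8.5.5.1 then compares event and duration rates before and after UX007, with study period 3 as the pre period. The post period is set by follow-up status:

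- **Longer-followed subjects.** "For subjects who had longer than 18 months of follow up on study (CL202) as of the data cutoff date", the rule is "MCEs that occurred between UX007 initiation and 18 months post UX007 initiation will be included for calculating number of MCEs".
- **Early terminators.** "For subjects who terminated the study prior to reaching 18 months on study, MCEs that occurred between UX007 initiation and the termination visit" are counted, with no cap stated.
- **Still on study at the cutoff with 18 months or less in CL202.** Nothing is stated.

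For the history, "the data collection period is 18 months (548 days) preceding the date of UX007 initiation". The same section also plans descriptive rates for the pre period, for CL201 and for CL202: "Within study period 1, annualized event/duration rates will be calculated by 18-month time interval". Box plots and patient-level event plots accompany these.

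**The concern.** The window paragraph in 8.5.5.1 nearly repeats the one written for the naive cohort in 8.5.4.1. Naive subjects start UX007 on CL202 study day 1, so time on study and time since initiation are the same clock. For rollover subjects the two clocks differ by the length of CL201. The paragraph tests eligibility for the cap on the CL202 clock but counts events on the CL201 clock.

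Followed literally, subjects who stay in CL202 contribute CL201 and almost nothing else. CL202 events would enter mainly from those who leave early. Window length then depends on dropout, and the pooled subjects represent different stretches of treatment. If the effect persisted or waned in CL202, this contrast would not show it.

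The sensitivity analyses in 8.5.5.2 inherit the unclear post period. The negative binomial text (8.5.5.2.1) states no cap, but its offset is only each subject's time in the study. The naive version (8.5.4.2.1) ties that phrase to study period 1, which for rollover subjects would leave out CL201.

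**Working it through.** **Locating UX007 initiation for rollover subjects**

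1. SAP 8.5.5.1 places the 548-day history immediately before UX007 initiation.
2. SAP 5.10.3 says the same history "starts from the 18 months (548 days) preceding UX007 treatment day 1" and ends the day before it.
3. SAP 5.4: "For subjects who rolled over from UX007-CL201, UX007 treatment day 1 is the day of the first UX007 dose during the UX007-CL201 study".

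UX007 initiation is therefore the first CL201 dose.

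**Inputs**

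- One month is 30.4375 days (SAP 5.5). The plan's own window reproduces: 18 × 30.4375 = 547.9, or 548 days.
- CL201 was 24 + 54 weeks (Protocol 5): 78 × 7 = 546 days.
- CL202 study day 1 coincides with the last CL201 visit (SAP 5.3), so there is no gap.
- CL202 lasts up to 84 months (SAP 3.3).

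**CL202 time inside the cap**

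548 − 546 = 2 days. This is nominal: if the last CL201 visit fell up to 14 days early or late (an assumed range), the figure would run from 16 down to 0.

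**Share of study period 2 used for capped subjects**

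Study period 2 = 546 + 30.4375 × T days, where T is months in CL202.

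| T (months) | Study period 2 (days) | 548 / period 2 |
|---|---|---|
| 24 | 1,276 | 43% |
| 36 | 1,642 | 33% |
| 60 | 2,372 | 23% |
| 84 | 3,103 | 18% |

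As a share of CL202 time, 2/730 = 0.27% at 24 months and 2/2,557 = 0.08% at 84 months.

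**Window for early terminators**

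Uncapped, 546 + 30.4375 × T gives 729 days at T = 6, 911 at T = 12 and 1,063 at T = 17. Just under 18 months it is 546 + 547 = 1,093 days (35.9 months). Just above 18 months the rule drops to 548 days.

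**Illustration of the effect on the result**

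The rate ratios against history are assumed, not taken from the documents: 0.5 during CL201 and r during CL202.

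- Capped: (546 × 0.5 + 2r) / 548
- Study period 2: (546 × 0.5 + 30.4375 T r) / (546 + 30.4375 T)

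| r in CL202 | Capped | Period 2, T = 24 | T = 36 | T = 84 |
|---|---|---|---|---|
| 0.5 | 0.50 | 0.50 | 0.50 | 0.50 |
| 0.8 | 0.50 | 0.67 | 0.70 | 0.75 |
| 1.0 | 0.50 | 0.79 | 0.83 | 0.91 |

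Even complete loss of effect in CL202 leaves the capped figure at 0.50.

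**The case against.** **A CL202 anchor may have been meant.** UX007 initiation is not a defined term, and the capping sentence carries a CL202 qualifier. On that reading the 2-day figure, the shares above and the long early-terminator windows all fall away. But the 548 days before initiation would then be on-treatment CL201 time, which contradicts study period 3 in the same section. The window would also be one 18-month block of CL202 with no CL201 data, so it would still not be study period 2.

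**A matched 18-versus-18-month comparison is reasonable.** It mirrors the naive cohort and the 78-week comparison reported for CL201, and its days do lie inside study period 2. As a design this has merit, but the text does not deliver it: early terminators are uncapped and one group has no rule.

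**Durability is covered elsewhere.** This largely stands. Rates for the pre period, CL201 and each 18-month interval of CL202 will be tabulated and plotted. SAP 8.5.5.1 names no test, and Table 11.1.1 lists only descriptive statistics for these rows. The negative binomial model can be read as using all follow-up. These points limit the damage, but they do not make the pre/post contrast itself coherent.

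**Study period 2 makes the periods unequal.** Post time would reach about 8.5 years against 1.5 years before, and its length would still vary with entry date and dropout. This is true, and it is why block contrasts belong beside the pooled one.

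**Conclusion.** The concern holds. As written, the post window for rollover subjects with more than 18 months in CL202 is CL201 plus about 2 nominal days, which is 43% down to 18% of the assigned period for 24 to 84 months of CL202 follow-up. Early terminators contribute up to about twice that window, and one group is undefined.

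The day counts rest on the nominal 78-week length of CL201 and on the first-CL201-dose anchor, which the SAP's own definitions support. The shift in the estimated reduction cannot be sized, because the documents give neither the rollover cohort size nor the follow-up distribution; the rate-ratio table is illustrative only.

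The defect is confined to this supportive comparison and to the sensitivity analyses that inherit its post period. It should be fixed, but it does not threaten the primary analysis.

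**What to change.** In SAP 8.5.5.1, delete the 18-month cap and the separate early-terminator window. Define the post-UX007 period for every rollover subject, including those still on study at the cutoff, as study period 2 limited to observed MCE follow-up. It should end at the data cutoff or the early termination or study completion visit, as SAP 5.11 already does for study period 1, with the subject's own days as denominator.

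Alongside it, report the pre/post contrast for each 18-month block already planned (CL201, then CL202 months 0–18, 18–36 and so on), with the number of subjects in each. Pooling then cannot hide waning, and the unequal period lengths are offset.

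State the same post period and offset in 8.5.5.2 and Table 11.1.1.

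The cost is SAP wording and some re-running of programs. The pooled reduction may look less favourable than under the capped rule.
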